2. STUDY PROCEDURES

a. Procedures

We will recruit a total of 30 participants.

All participants will receive intermittent theta burst (iTBS) over L DLPFC (five days 10x/day).

Participants will have moderately treatment resistant major depressive disorder as defined by a score of ≥ 20 on the HAMD-17, MADRS and BDI-II scales.

Screening Time-Period:

Patients will undergo a screening time period where their eligibility will be confirmed. This may occur any time prior to the baseline time period. Following screening informed consent, clinical interviews and behavioral testing will occur at the Stanford Psychiatry

department. The clinical interview will include a screen for inclusion and exclusion criteria, MRI safety, TASS, medical and psychiatric history, neurological exam, urine tox screen, pregnancy test, and motor threshold (see Motor Threshold section for details below).

Diagnosis will be confirmed with the MINI and/or SCID. We will also request medical records to confirm information collected during the screening visit. Patients will be staged using the Maudsley staging method and a trained rater will perform: HAMD-21, MADRS, ATHF, YMRS and SSI.

Patients will fill out self-reports including the BDI-II and C- SSRS.

Baseline Time-Period:

Baseline visits will be separate from screening visits to confirm stability of symptoms (stability is defined as a difference in MADRS score below 30% from screening).

Participants will have an MRI scan in the morning.

Baseline clinical measures (MADRS and HAMD-17) will be performed. In addition, patients will fill out the C-SSRS self-report.

Participants will practice using the heart rate monitor that they will be using for the remainder of the study.

Active Study Time-Period:

iTBS sessions will be scheduled in a 5-day sequence, resulting in a total of 50 sessions over 5 days. Participants will receive 10 daily stimulations. Each session is separated by a 50-minute break. This separation between sessions decreases the risk of associated TMS side effects (e.g. irritation from the device, headache).

Follow-up Time-Period:

Patients will have the same clinical assessments as well as MRI scans that were completed during the baseline time-period at the immediate post-treatment and 1-month post-treatment mark. Heart rate will be measured during these time points.

Motor threshold:

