Using single pulse TMS, the scalp position of lowest motor threshold for the right first dorsal interosseous or abductor pollicis brevis muscles will be determined.

Resting motor threshold (MT) was defined using the Adaptive Pest online algorithm.

Participants in the active stimulation group will receive intermittent TBS (intermittent TBS-1800 pulses/session). They will receive 1800 stimuli of iTBS to left DLPFC per session.

The L-DLPFC will be targeted utilizing the Localite neuronavigation system.

Stimulation intensity will be standardized at 90% of RMT and adjusted to the skull to cortical surface distance (see Nahas 2004). Sessions will be delivered using the MagPro stimulator, with 3-pulse 50-Hz bursts given every 200ms (at 5 Hz). In the intermittent TBS, a 2s train of bursts will be given every 10 s for a total of 570s (1800 pulses) over the L DLPFC.

Heart Rate Monitors:

We will monitor heart rate and heart rate variability at all or some of the established time points for the active study in order to assess how aiTBS stimulation affects heart rate. Some participants may have to shave areas of their chest in order for the heart rate monitor electrodes to stick in place.

Imaging and Biomarkers:

We will acquire MRI scan sequences prior to active study phase, immediately after active study phase (1-3 days following final aTBS stimulation), and at one-month post-stimulation (between 25-30 days following the final aTBS stimulation). At the acute phase, we will acquire structural scans and functional scans at the CNI on the Stanford campus.

Functional Neuroimaging:

First-level models: We will use a canonical hemodynamic response function (HRF) convolved event-related model with temporal and dispersion derivatives to model the blood oxygen level dependent (BOLD) in the context of a generalized linear model. Separate regressors (convolved with the HRF) will be created for stimulus events in each paradigm. Temporal and dispersion derivatives will be treated as regressors of no interest. A region of interest (ROI) analysis will be performed using our established methods, to identify BOLD-dependent signal change in the dorsolateral prefrontal cortex, subgenual cingulate, and default mode network nodes (right, left). Beta values for each ROI will be extracted for each subject for regression analyses.

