The subjects will undergo an MRI scan of the brain that will require about 1 hour in the MRI scanner. A structural MRI scan and an fMRI scan will be done using a 3T system at Stanford facilities.

During the scan, subjects will lie on the table in the magnet for 1 hour while the images are acquired. Instructions may be given through an auditory system. Subjects will wear earplugs and may be fitted for a bite bar to help them to keep their head still during the scans; for studies that enroll older adults, a bite bar will not be used so as to accommodate participants with dentures. These procedures have been used previously in younger and older adults alike, and do not cause undue distress in subjects. Brain images will be made using conventional MRI imaging (including functional and diffusion tensor

imaging).

Patients will undergo a minimum of 3 scans up to a maximum of 6 scans, each 1 hour in length.

Acquisition and data extraction:

Clinical interview ratings will be made by trained study personnel. Individual item scores will be recorded and then summed according to symptom cluster and scale definitions.

Outcome measures:

The primary outcome measure for this study will be change in MADRS score. The MADRS is a clinical assessment tool used to rate a patient's level of depression and is the standard scale used for depression research studies.

Secondary measures will include functional connectivity change of the sgACC to the DMN. Primary outcome will be assessed as the change between baseline and immediate post-stimulation, with secondary measures to include the change between baseline and immediate post- stimulation and 1-month post-stimulation.

Other secondary measures include clinical interview assessments, to be performed according to the timeline above, include:

HAMD-17 (Hamilton Depression Rating Scale 17-Item)
C-SSRS (Columbia Suicide Severity Rating Scale)
HAMD-6 (Hamilton Depression Rating Scale 6-Item)
MADRS (Montgomery-Asberg Depression Rating Scale)

b. Procedure Risks

These methods are the least risky because the intervals of stimulation have been shown to be appropriate for theta burst stimulation in the motor system with no adverse outcomes.

We don't anticipate any risk from the procedures themselves, aside from those mentioned in section 7a i.

c. Use of Deception in the Study

NA

d. Use of Audio and Video Recordings

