Rationale for Study Design: The design will allow to assess the feasibility of modulating the neural circuitry underlying depression with accelerated intermittent theta-burst stimulation (aiTBS) alongwith the measuring the effects of this neuromodulation strategy on the underlying neural circuitry. The same subjects are utilized for all three MRI scan sessions, that is, for the pre-aiTBS scan session, the immediate post-aiTBS scan session and for the 1-month post-aiTBS follow-up scansession (to address functional connectivity aims). The rationale for using the same subject threetimes is to enable analysis of functional connectivity differences in the left DLPFC and dACC in response to aiTBS across time.

Sample Size

The study will be powered for an estimated effect size of Cohen's $d=0.6$ for change in Montgomery-Åsberg Depression Rating Scale (MADRS) between baseline and one month post treatment using within subject t-test. Prior investigations of iTBS of the L-DLPFC for treatment resistant depression reported an effect size of $d=1.337$, leaving our estimate conservative. We will set the probability of rejecting a true null hypothesis (Type 1 error, alpha) at 0.05 (two-sided) with 80% power. That will require a final sample size of 23 participants. This study will aim to recruit 30 individuals assuming approximately 20% missing data due to unusable imaging data or dropouts.

Interim Analyses and Stopping Rules

Because of the anticipated low level of adverse events of aiTBS and MRI, interim analysis of data,protocol and adverse events will occur by study staff at least once a year. Serious adverse events will be reviewed on a monthly basis, unless a more urgent review is requested. Only under extreme circumstances or if it were determined that a high level of side effects was due to aiTBS and/or MRI, would the PI be charged with breaking the study mask. This study will be stopped prior to its completion if: [1] the intervention is associated with adverse effects that call into question the safety of the intervention; [2] difficulty in study recruitment or retention will significantly impact the ability to evaluate the study endpoints; [3] any new information becomes available during the trial that necessitates stopping the study; or [4] other situations occur that might warrant stopping the study.

Data Analyses

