The Primary Mechanistic Outcome Measure for this study is percent change in MADRS scoreat one-month post treatment. **The Relevant Clinical Outcome Measure** is a reduction in depressive symptoms in treatment resistant outpatients diagnosed with MDD, as measured

by change in MADRS score. For secondary aims, the emphasis is on identifying the magnitude of effects (clinical significance, effect size) instead of statistical significance. Following the convention in imaging studies, we will conduct our primary analyses treating the contrast (baseline versus post) as one univariate outcome. We do not expect much variation across our narrowly defined subjects, although some variation is still possible. Given that, we will also analyze the data in the linear mixed effects modeling framework allowing for random intercepts (although this is not customary in imaging studies) as a way of sensitivity analysis.

Moderator/mediator investigation: We will explore various baseline variables as potential moderators of aiTBS. For this investigation, we will employ the MacArthur approach for moderator analysis. We will also examine potential mediators of rTMS effect using the MacArthur approach as well as contemporary causal mediation approaches, which we believe will provide valuable insights regarding the neuromodulation mechanism for the next phase of investigation.

Handling of missing data: As a way of assessing the impact of missing scan sessions, we will repeat our main analyses treating outcomes measured in the pre-aiTBS scan and in the 1-month post-aiTBS scan as multivariate outcomes. This will allow us to include all participants in the analysis as long as two of the three scans are available. In this analysis framework, missing data will be handled assuming that it is missing at random conditional on observed scan session data (maximum likelihood estimation). Analyzing the data using both univariate and multivariate analysis approaches will also serve as sensitivity analyses. Additionally, we will include the order of scan sessions in the model to account for the carryover and order effects.

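### The missing-scan sensitivity analysis adjusts for scan order, but everyone is scanned in the same sequence, so order duplicates visit and cannot remove carryover or order effects

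*SAP*

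**What the plan says.** The sentence is in SAP section 9, Data Analyses, under the handling of missing data. That paragraph sets its own scope: "As a way of assessing the impact of missing scan sessions, we will repeat our main analyses", with the pre-treatment and 1-month scans treated as joint outcomes, fitted by maximum likelihood under missing at random, for participants who have two of the three scans. It ends: "we will include the order of scan sessions in the model to account for the carryover and order effects". The SAP does not define order.

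The design is described elsewhere:

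- Protocol section 2a, one arm: "All participants will receive intermittent theta burst (iTBS) over L DLPFC".
- SAP section 9, Rationale for Study Design: "The same subjects are utilized for all three MRI scan sessions", listed as pre-treatment, immediate post-treatment and 1-month follow-up.
- Protocol section 2a, Imaging and Biomarkers: "We will acquire MRI scan sequences prior to active study phase, immediately after active study phase" (1–3 days after the last stimulation), then a third scan at 25–30 days.
- Protocol section 2a also says: "Patients will undergo a minimum of 3 scans up to a maximum of 6 scans". It gives no times for scans beyond the three.

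Neither document describes a second condition, a crossover or a counterbalanced scan order.

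**The concern.** A model can adjust for order or carryover only if order varies separately from the effect of interest, as in a crossover with more than one sequence. Here the scan windows do not overlap and treatment always falls between the first and second scans. Any effect of being scanned again is confounded with the effect of treatment.

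Two things are at stake for Secondary Objective A. First, if visit and order are both entered, the reported visit coefficient depends on how order is coded or which column the software drops, so read alone it is not the pre-post change. Second, the SAP commits the report to saying that carryover and order were accounted for, which this design cannot support. A reader weighing an uncontrolled pre-post imaging change could be wrongly reassured.

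**Working it through.** The plan gives no figure for this term, so the check is on the design matrix.

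**Inputs.** From the documents: 30 participants, one arm, three ordered scans. The SAP's Sample Size paragraph sets recruitment "assuming approximately 20% missing data due to unusable imaging data or dropouts"; 20% of 30 is 6. Assumed here, because the documents do not give them: a random-intercept model with unit variance, within-participant correlation r = 0.3, 0.5 or 0.7, and which scan the 6 participants miss. The paragraph names the pre and 1-month scans but counts three sessions for inclusion, so both models were checked.

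**Step 1: order as scheduled position.** For every participant, order = 1 + 1 × [immediate] + 2 × [1 month]. The column is an exact combination of the intercept and the visit indicators.

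| Model | Columns | Rank |
|---|---|---|
| Three visits, no order | 3 | 3 |
| Three visits + numeric order | 4 | 3 |
| Three visits + categorical order | 5 | 3 |
| Pre and 1 month, no order | 2 | 2 |
| Pre and 1 month + order | 3 | 2 |

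Missing scans do not change this while order means scheduled position. In the three-visit model with numeric order, the contrast (1-month visit coefficient + 2 × order coefficient), which is the total pre-to-1-month change, lies in the row space and is estimable. The 1-month visit coefficient alone does not and is not.

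**Step 2: reading (a), order as the nth scan attended.** Suppose 6 of 30 miss only the immediate scan. Their 1-month scan is number 2; for the other 24 it is number 3. The model is now full rank (4 of 4 with three visits, 3 of 3 with two), but only because of who missed a scan.

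- Without order, the variance of the pre-to-1-month change is 2(1 − r)/30.
- The order coefficient rests on comparing the groups of 24 and 6. Its variance is (1 − r²)(1/24 + 1/6) = 0.2083(1 − r²).
- The mean order step is (24 × 2 + 6 × 1)/30 = 1.8. The visit coefficient at fixed order therefore has variance 2(1 − r)/30 + 1.8² × 0.2083(1 − r²) = 2(1 − r)/30 + 0.675(1 − r²).
- Ratio to the model without order: 1 + 10.125(1 + r) = 14.2, 16.2 and 18.2 for r = 0.3, 0.5 and 0.7. Standard errors are 3.8 to 4.3 times as large.
- The total change for someone attending all three scans (step 2) has ratio 1 + 0.2² × 0.2083(1 − r²) × 15/(1 − r) = 1 + 0.125(1 + r) = 1.16, 1.19 and 1.21. At the mean step of 1.8 the ratio is 1.00.

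The ratios are the same in the two-visit model. If the 6 instead miss the 1-month scan, rank returns to 3 of 4. If scans are attended but unusable, attendance order still equals visit and the rank is again 3 of 4.

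**Step 3: reading (b), linear order plus one pre/post indicator.** Rank is 3 of 3. Write y1, y2, y3 for the three scans. Without order the effect is (y2 + y3)/2 − y1, with variance 1.5(1 − r)/30. With order it is (y2 − y1) − (y3 − y2) = 2·y2 − y1 − y3, with variance 6(1 − r)/30. The ratio is 4.0 at every r. This reading also has to assume that the treatment effect is equal at both post-treatment scans.

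**The case against.** The strongest reply is that little goes wrong in practice. A fully aliased column changes neither the fitted values, nor the likelihood, nor the total pre-to-1-month change, which is what the SAP wants. Software drops the column, and harm follows only if someone reports the raw coefficient. That is right about the total contrast. It does not rescue the stated purpose: a term with no effect on the fit accounts for nothing.

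The large variance ratios can also be challenged. They apply to the order-adjusted visit coefficient, not to the total change, whose variance rises at most 1.21-fold in reading (a). The missingness pattern in (a), skipping only the immediate scan, is not the one the SAP has in mind, and (b) is not proposed anywhere. All of this stands. The ratios show only what happens if the term is made estimable; the aliasing does not rest on them.

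The allowance of up to six scans leaves some doubt about a strictly common sequence. If some participants had a repeat pre-treatment scan, a retest effect might be partly estimable. No such scan is scheduled, however, and the SAP models three sessions.

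Finally, this is a sensitivity analysis of an exploratory secondary objective. That limits the importance of the point but does not make the sentence correct.

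**Conclusion.** The concern holds. As written, the SAP promises an adjustment that the design cannot provide. With order as scheduled position, the term adds no rank to visit in either the three-visit or the two-visit model; this needs no assumption beyond the single sequence both documents describe. The 14- to 18-fold and 4-fold variance increases apply only to the order-adjusted visit coefficient, under readings the SAP does not state and with the assumed correlations and missingness. Even there, carryover and order are not credibly separated from treatment.

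The reach is limited to the missing-scan sensitivity analysis of sgACC–DMN connectivity. The MADRS within-subject t-test and the sample size contain no order term, and the univariate baseline-versus-post imaging contrast as specified is untouched. The sentence should be corrected, but the primary result does not depend on it.

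**What to change.** Delete the sentence on scan order, and the term, from the missing-data paragraph of SAP section 9. Keep visit as a categorical time effect and report the visit contrasts. Add a statement that, in a single-arm study with one scan sequence, repeat-scan and order effects cannot be separated from the effect of treatment, and carry it into the report as a limitation.

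The cost is a small edit to one paragraph. Nothing estimable under the scheduled sequence is lost; the report only gives up a claim of adjustment for carryover and order that it could not have supported.
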